### 12.2 Serious Adverse Events (SAE)

A serious adverse event (SAE) is defined as any untoward medical occurrence that:

- Is life threatening or results in death.
- Requires in-patient hospitalization or prolongs existing hospitalization.
- Results in persistent or significant disability/incapacity.
- Is a congenital abnormality/birth defect (in the offspring of a participant).
- Jeopardizes participant and required medical/surgical intervention to prevent serious outcome, *or*
- Any other event that the investigator considers serious.

### **12.2.1 Serious Adverse Event Reporting**

Study sites will document all SAEs that occur (whether or not related to study drug) per [UCSF IRB Guidelines](#). The collection period for all SAEs will begin after informed consent is obtained and end six weeks after the visit where Mifeprex® is prescribed.

In accordance with the standard operating procedures and policies of the local IRB/the site PI will report SAEs to the IRB.

## **13 DISCONTINUATION AND REPLACEMENT OF SUBJECTS**

### **13.1 Early Discontinuation of Study Drug**

Because participants will only take a single dose of Mifeprex®, there will be no opportunity to discontinue treatment. If a patient vomits within 30 minutes after taking Mifeprex®, she will be instructed to return to the clinic site for further evaluation and management.

### **13.2 Withdrawal of Subjects from the Study**

A subject may be withdrawn from the study at any time if the subject, the site PI, or the PI feels that it is not in the subject's best interest to continue.

All subjects are free to withdraw from participation at any time, for any reason, specified or unspecified, and without prejudice.

Reasonable attempts will be made by the site PI to provide a reason for subject withdrawals. The reason for the subject's withdrawal from the study, and reasons for any early discontinuation of participation in the study, will be specified in the subject's data collection documents.

### **13.3 Replacement of Subjects**

If any subject withdraws prior to taking the medications, an additional subject will be recruited to maintain the initial target sample and this will be included in the final report. If a subject withdraws after taking any of the medications and does not complete follow-up, they will be reported as lost to follow-up.

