### **10.2 Day 3 Survey**

On Day 3 (after the prescription is sent), patient participants will be sent by email or text message, depending on their preference, a link to an online survey about their experience receiving the medications, as well as to collect sociodemographic information (see Day 3 survey). If a participant prefers, or if she does not respond to the email link, she may be contacted by telephone to complete the survey over the phone or sent reminders by text message. The survey will focus on her experience receiving the medications by mail, including whether and when she received the medications and the quality of the packaging, as well as her experience taking the Mifeprex®. We will also collect

information about if and when the Mifeprex® and misoprostol might have been diverted to another person. If they do not respond to the survey within two days, participants will be contacted by telephone or text message up to three times. If a participant has decided not to proceed with medication abortion (for any reason), she will be encouraged to complete the Day 3 survey, where this information will be captured. If a woman obtained the Mifeprex® and/or misoprostol and has decided not to take the medication(s), she will be asked to return them to the clinic.

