### **10.4 Day 14 Survey**

On Day 14 after the prescription is sent, patient participants will be sent by email or text message, depending on their preference, a link to an online survey about their overall satisfaction with the medication abortion process and to obtain information about whether the abortion has been completed (see Day 14 Survey), and whether she has sought care at another facility. If she did obtain care at another facility, we will ask for details of the care given to determine if an AE or SAE has occurred, and we will follow up with the participant by telephone to obtain additional details as needed. If the participant reports being seen at another facility, we will alert the site PI. If a participant prefers, or if she does not respond to the email link, she may be contacted by telephone to complete the survey over the phone or sent reminders by text message. If the follow-up for the abortion is not yet complete at the Day 14 survey, we will instruct the patient to contact the clinic and ask for permission to contact them again later. If they do not respond to the Day 14 survey, participants will be contacted up to three times.

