### 16.1 Data Sets Analyzed

All eligible patients who receive the dose of the study drug will be included in the analysis. All eligible providers who complete an interview will be included in the provider analysis.

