### 16.3 Analysis of Primary Endpoint

Acceptability and satisfaction with the mail-order model among patients will be assessed through patient surveys, which will include some open-ended items. The particular variables we will analyze include those on overall satisfaction with the medication abortion service (including whether they would use this mail-order medication abortion service again if they needed another abortion, and whether they would recommend the service to a friend), satisfaction with receiving the medications by mail, reasons for dissatisfaction (open ended questions), and perceptions about the wait time to receive the medications. We will also analyze the reasons why patients who decline participation in the study report not being interested in receiving the medications by mail, as indicated in close-ended and open-ended responses.

We plan to recruit for the main study a minimum sample of 440 participants and a maximum of 625 patients. With the addition of 25 patients in the pilot study, the target minimum number of patients recruited for the study is 465 and the maximum number is 650.

The sample size calculation for this study is based on two measures of acceptability: the proportion of patients who report they would use medication abortion again if they needed another abortion and the proportion who report they were “satisfied” or “very satisfied” with the medication abortion. For both power calculations, we assume 10% loss to follow up, 10% adjustment for clustering, a 5% non-inferiority margin, and a two-sided alpha of 0.05. Research with patients obtaining clinic-based medication abortion has estimated the proportion who would use medication abortion again as 89.7% (Teal, Dempsey-Fanning et al. 2007). Based on our assumptions, with a minimum sample of 440 patients, we will have a final analytic sample of approximately 400 patients, which gives us 79% power to assess this measure of acceptability; with a maximum sample of 625 recruited patients, we will have a final analytic sample of approximately 560 patients, which gives us 92% power.

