## 16.4 Analysis of Secondary Endpoints

Feasibility of the mail-order pharmacy dispensing model will be assessed through surveys with patients, and include determination of the proportion of patients who receive the medications by Day 2 and by Day 3 after the prescription is sent, the quality of the packaging, whether patient confidentiality was compromised due to receiving the medications by mail, as well as the proportion of patients who had to go to the clinic to obtain the medications.

Clinical effectiveness and safety outcomes, including adverse events, with medication abortion obtained via mail-order pharmacy will be assessed using quantitative data abstracted from patient medical records, as well as information on clinical outcomes captured in the Day 14 patient survey. The analysis populations for the effectiveness and safety endpoints will include patients who enroll in the study, take either of the medications, and for whom we have follow-up data. We will not assume that patients who do not have follow-up data had a successful abortion.

Effectiveness will be defined as the successful completion of abortion (versus incomplete abortion or continuing pregnancy), without vacuum aspiration. Continuing pregnancy will be defined as a viable pregnancy following treatment and need for vacuum aspiration to terminate the pregnancy or cases where a patient elects to continue the pregnancy after failed treatment (Creinin & Chen 2016). We will document vacuum aspiration abortions, including reasons for aspiration, reported by participants and those determined as necessary by the study providers at follow-up visits. We will compare effectiveness (the proportion of our sample that experiences a complete abortion not requiring vacuum aspiration) with published estimates (97.4%) (FDA 2016), using an exact binomial test. Assuming 10% loss to follow-up and 10% adjustment for clustering, and a two-sided alpha of 0.025 (to account for type I error), we estimate that a final analytic sample ranging from approximately 400 to 560 patients gives us 98% to 100% power to determine that mail-order medication abortion is as effective as in-person dispensing, if effectiveness in the mail-order model is no lower than 92.4%. A non-inferiority limit is defined as -5% and as an acceptable difference in the proportion of complete abortions.

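### The primary acceptability proportion leaves out patients who drop out of the mail service before getting the drug, and no analysis puts them back

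*Combined protocol and SAP*

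**What the plan says.** Section 16.1 sets one rule for patients: "All eligible patients who receive the dose of the study drug will be included in the analysis". Section 16.3 lists the acceptability items, including whether the patient would use the mail-order service again and whether she was satisfied with delivery by mail, but names no analysis population. Section 16.4 does define one, for effectiveness and safety only: patients who enrol, "take either of the medications, and for whom we have follow-up data".

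Section 13.3 deals with patients who leave before intake: "If any subject withdraws prior to taking the medications, an additional subject will be recruited to maintain the initial target sample". Such replacements are to be disclosed when the study is reported. The section does not say whether the original patient stays in any analysis.

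On data collection, section 10.2 says of a patient who decides not to proceed that "she will be encouraged to complete the Day 3 survey, where this information will be captured". That survey is described as covering receipt, packaging and taking the drug. Section 10.4 places "an online survey about their overall satisfaction with the medication abortion process" at Day 14, counted from the prescription. The use-again and satisfaction-with-mail items are not assigned to either survey.

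The test compares acceptability with a historical 89.7%, using "a 5% non-inferiority margin, and a two-sided alpha of 0.05" (section 16.3).

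**The concern.** The primary endpoint is meant to show whether patients accept getting the medication by mail. Much of that experience falls between the prescription and intake: the wait, the delivery, the packaging, privacy at the address. A patient put off by any of these may leave in that window. The plan itself provides exits there. Section 6.1 refers patients without medication within 3 days elsewhere, or back to the site where abortion is already provided. Section 14.1 encourages patients without medication on Day 3 to make other arrangements. Section 5 expects to include clinics that do not stock mifepristone, so a patient who leaves may never get the study dose at all.

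Section 16.1 then makes getting the dose a condition of being counted. If the patients lost this way would more often say no, the reported proportion is too high, and it is compared with a limit only 5 points below the benchmark.

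**Working it through.** **Inputs from the documents (sections 16.3 and 16.6).** Benchmark 89.7%; margin 5 points, so the limit is 89.7 − 5 = 84.7%; two-sided alpha 0.05, that is 0.025 on the non-inferiority side; about 400 or 560 analysed; 10% clustering adjustment; stated power 79% and 92%.

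**Assumed inputs.** w is the share of patients with a prescription sent who leave before intake for mail-related reasons and fall outside the analysed set. q is the share of these who would use the service again. The documents give neither. Other withdrawals are taken to resemble the analysed patients.

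**1. The plan's own power.** One-sample test against a fixed limit, normal approximation, with n = 400/1.10 = 364 and 560/1.10 = 509:

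power = Φ{[(p1 − p0) − 1.96·√(p0(1 − p0)/n)] / √(p1(1 − p1)/n)}, p0 = 0.847, p1 = 0.897.

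- n = 364: (0.05 − 1.96 × 0.01887)/0.01593 = 0.817, power 79.3% (stated 79%).
- n = 509: power 91.8% (stated 92%).

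The power figures reproduce. The question is who is in the denominator.

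**2. Acceptability with the missing patients included.** If 89.7% of the analysed patients accept, the all-prescribed value is (1 − w) × 0.897 + w × q.

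| w | q | All-prescribed acceptability |
|---|---|---|
| 5% | 50% | 87.7% |
| 5% | 30% | 86.7% |
| 8% | 30% | 84.9% |
| 10% | 30% | 83.7% |

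The section 16.1 set shows 89.7% in every row. Only the last row is below 84.7%.

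**3. Break-even.** The whole margin is used when w × (0.897 − q) = 0.05, so w = 0.05/(0.897 − q):

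- q = 0: 0.05/0.897 = 5.6%, about 24 such patients beside 400 analysed.
- q = 30%: 0.05/0.597 = 8.4%, about 37.
- q = 50%: 0.05/0.397 = 12.6%, about 58.

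**4. Error rate of the test.** Set true all-prescribed acceptability at the limit. Among the analysed it is then (0.847 − q·w)/(1 − w). An exact binomial test with n = 364 declares non-inferiority at 322 or more acceptors. The chance of doing so wrongly is:

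| w | q = 0 | q = 30% |
|---|---|---|
| 0% | 2.4% | 2.4% |
| 2% | 14.5% | 8.2% |
| 3% | 28.7% | 14.0% |
| 5% | 70.1% | 33.9% |

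The error rate thus rises well before the margin is used up.

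**5. The role of replacement.** The formula in step 2 has no replacement term. Recruiting another patient changes n, not the expected proportion among those analysed. The exclusion comes from section 16.1.

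**The case against.** The strongest reply is that the exclusion is narrower than it looks. Section 8.6 separates patients who received mifepristone from those who took it, and section 16.4 says *take* where takers are meant. If *receive* in section 16.1 means delivered, a patient who got the package and did not use it is already in the set. That stands: only patients who never get the drug are outside on any reading, and w may be small.

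A reader might infer from section 13.3 that replacement swaps patients who gave up on the mail service for patients for whom it worked. The documents do not support this. Section 13.3 adds a subject and does not delete one; replacements are ordinary new enrolees; and withdrawal may be for any reason (section 13.2). Nor is late delivery the same as withdrawal: a patient who then gets the drug at the site may still be analysed and report dissatisfaction.

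A reader might also infer that patients who stop early are never asked about satisfaction. But section 10.4 sends the Day 14 survey to participants by prescription date, without excluding non-takers. Some answers may therefore exist; what is missing is a rule that uses them.

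There are safeguards. Withdrawal reasons are recorded (13.2), referrals and returns counted (6.1), replacements reported (13.3), receipt by Day 2 and Day 3 analysed as feasibility (16.4), and long delays trigger investigation or a temporary halt (14.1). These make the problem visible, but none returns a patient to the primary proportion.

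Finally, the benchmarks come from patients who had the abortion: clinic-based for 89.7% and home-based for 88.4%. An all-prescribed set does not match them exactly. That is a fair reason not to insist that it replace the section 16.1 set as primary.

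**Conclusion.** The point holds as a gap in the analysis population. Under sections 16.1 and 16.3, patients who leave without getting the drug do not count in the primary acceptability proportion, those who get it and do not take it may not count either, and no analysis of all prescribed patients is described.

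The expected direction is upward, provided that the missing patients are less accepting than those analysed. It would be too strong to say that the bias can only favour the mail-order model, since that depends on q being below 89.7%. The size cannot be fixed from the documents. The margin is used up at w of 5.6% to 12.6% for q from 0 to 50%. At n = 364, w of 2% to 3% raises the error rate from 2.4% to between 8.2% and 28.7% for q from 30% down to 0. If few patients leave for mail-related reasons, the effect is small.

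**What to change.** The plan promises a detailed SAP before the final analysis (section 16), so there is room to settle this.

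1. In sections 16.1 and 16.3, state whether *receive* means delivered or taken. Add an acceptability analysis on all eligible patients whose prescription was sent to the mail-order pharmacy, reported beside the section 16.1 set. Add a sensitivity analysis that counts withdrawals before intake for mail-related reasons as would not use again.
2. In section 13.3, state that replacement does not remove the original patient from the all-prescribed analysis, and report these withdrawals by reason.
3. Make sure that the use-again and satisfaction-with-mail items reach patients who stop before intake, at Day 14 or as two items added to Day 3, unless they withdraw consent for contact.

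The cost is some wording and two survey items for a few more people, with no extra recruitment. The all-prescribed estimate may be slightly lower, and should carry the caveat that the benchmarks describe patients who had the abortion.

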## **14 PROTOCOL VIOLATIONS**

A protocol violation occurs when the subject, investigator, or clinic or pharmacy staff fails to adhere to significant protocol requirements affecting the inclusion, exclusion, subject safety and primary endpoint criteria. Potential protocol violations for this study include, but are not limited to, the following:

- Failure to meet inclusion/exclusion criteria
- Failure to comply with Good Clinical Practice (GCP) guidelines. The PI will determine if a protocol violation will result in withdrawal of a subject.

When a protocol violation occurs, it will be discussed with the site PI and a Protocol Violation Form detailing the violation will be generated. This form will be signed by the PI and the site PI. A copy of

the form will be filed in the site's regulatory binder and in the PI's files.

## 14.1 Study Stopping Criteria

The following criteria will be used to determine whether and when to stop the study prior to meeting recruitment targets:

- If there are 3 cases where mail-order delivery of the medication is delayed by more than 7 days, we will temporarily halt the study and assess the need to adjust the inclusion criteria to less than 57 days' gestation (instead of 63 days) in order to eliminate the possibility that participants receive mifepristone past 70 days' gestation. We will also investigate all cases of medication delivery being delivered more than 4 days after the prescription was sent to understand the factors that contributed to delay and address them. In addition, we will contact all participants on Day 3 after the prescription was sent, and if they have not received the medications, we will encourage them to contact the study site to make other arrangements to obtain the mifepristone and misoprostol.
- If there are 12 cases (3% of total sample) where the participant takes mifepristone after 70 days' gestation, we will assess the need to stop the study. All cases of use past 70 days will be investigated to understand why they occurred and efforts will be made to ensure such errors do not occur in the future. There is evidence that the medication abortion regimen works through 11 weeks of gestation (Kapp, Eckersberger et al. 2019); with regard to clinical safety, this is why the research team feels comfortable with 12 potential cases beyond 70 days gestation. Finally, if 1% of participants (4 cases) take the mifepristone after 84 days (12 weeks), we will stop the study.
- Every AE and SAE will be reviewed by the study PI, and if there is a pattern of definitely-, probably-, or possibly-related SAE/AEs that raise concerns about the safety of the mail-order model of dispensing mifepristone, the study will be stopped. Based on evidence that 0.3% of medication abortions have serious adverse events (Upadhyay, Johns et al. 2018), we will stop the main study if the number of SAEs fall outside of a 95% confidence interval as estimated in a sample of 465 (-0.24% to 0.84%) (minimum sample of 440 plus 25 pilot study participants). Thus we will stop the study if more than 0.84% (n=4) of abortions result in an SAE that is possibly or probably related to the study intervention.

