## 16.6 Sample Size

In addition to the 25 patients in the pilot study, we aim to recruit a minimum of 440 and a maximum of 625 patients for this study, across 15-20 sites. The sample size calculation for this study is based on a measure of acceptability: the proportion of patients who report they would use medication abortion again if they needed another abortion. Research with patients obtaining clinic-based MA has estimated that proportion as 89.7% (Teal, Dempsey-Fanning et al. 2007). We would like to determine if acceptability of medication abortion when receiving the medications by mail is no more than 5% lower than 89.7%. Assuming 10% loss to follow-up, with a minimum sample of 440 patients, we will have a final analytic sample of approximately 400 patients; with a sample of 625 recruited patients, we will have a final analytic sample of approximately 560 patients. With a 2-sided alpha of 0.05 and 10% adjustment for clustering, a final analytic sample size of approximately 400 gives us 79% power, and an analytic sample of 560 gives us 92% power to assess this measure of acceptability.

We aim to interview all the providers (or staff administrators) involved in medication abortion provision at the study sites, up to 50. This sample size will be determined by the number of providers/staff at the study sites.

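### The late-intake thresholds in section 14.1 pair counts with percentages that match only at n = 400, which leaves the mandatory 84-day stop ambiguous at the planned 465 to 650

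*Combined protocol and SAP*

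**What the plan says.** Section 14.1 (Study Stopping Criteria) sets two thresholds for mifepristone taken late.

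- After 70 days: "If there are 12 cases (3% of total sample) where the participant takes mifepristone after 70 days" of gestation, the team will assess whether the study needs to stop. The count comes first and the percentage is in brackets. The rationale that follows repeats the count of 12 as the number the team is comfortable with.
- After 84 days: "if 1% of participants (4 cases) take the mifepristone after 84 days (12 weeks), we will stop the study". Here the percentage comes first and the count is in brackets. This is a stop, not a review.

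On sample size, section 16.3 says "the target minimum number of patients recruited for the study is 465 and the maximum number is 650". That is 440 to 625 in the main study plus 25 pilot patients. The figure of 400 appears only as what remains for analysis: "with a minimum sample of 440 patients, we will have a final analytic sample of approximately 400 patients". Section 16.6 gives the corresponding upper figure: "with a sample of 625 recruited patients, we will have a final analytic sample of approximately 560 patients".

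The SAE rule in the same list of section 14.1 names a different base, a "95% confidence interval as estimated in a sample of 465 (-0.24% to 0.84%) (minimum sample of 440 plus 25 pilot study participants").

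**The concern.** Each threshold is stated twice, and the two statements coincide only for a sample that is neither the total sample nor the participants as the protocol defines them. Where a rule is a mandatory stop and its two forms differ, the same data can require stopping on one reading and not on the other.

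That is the position for the 84-day rule. With 4 cases among 600 enrolled, the bracketed count has been reached, but the leading percentage has not (4/600 = 0.67%). Section 14.1 does not say which takes precedence. Nor does it say whether the 1% is taken of those enrolled so far or of the final total, although the criteria are meant to operate before recruitment targets are met. Section 2.1 places late intake within the main risk of the study, so the written trigger should have one meaning.

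**Working it through.** **Inputs.** 12 cases and 3%, 4 cases and 1% (section 14.1); total recruited 465 to 650 (section 16.3); analytic sample about 400 to about 560 (sections 16.3 and 16.6).

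**Step 1: the base that reproduces the printed pairs.** Implied n = cases / percentage.
- 12 / 0.03 = 400
- 4 / 0.01 = 400

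This is the approximate minimum analytic sample: 440 × 0.90 = 396, given in the protocol as about 400.

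**Step 2: the pairs at the planned sizes.** Printed count as a percentage = cases / n. First whole count that reaches the percentage = 3% × n or 1% × n, rounded up.

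| n | What it is | 12/n | First count at 3% | 4/n | First count at 1% |
|---|---|---|---|---|---|
| 400 | minimum analytic (approx.) | 3.0% | 12 | 1.0% | 4 |
| 465 | minimum recruited | 2.6% | 14 (13.95) | 0.9% | 5 (4.65) |
| 560 | maximum analytic (approx.) | 2.1% | 17 (16.8) | 0.7% | 6 (5.6) |
| 650 | maximum recruited | 1.8% | 20 (19.5) | 0.6% | 7 (6.5) |

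**Step 3: allowance for rounding.** If the percentages are whole numbers after rounding, 12 cases reads as 3% while 12/n is at least 2.5%, that is up to n = 12/0.025 = 480. Four cases reads as 1% from n = 4/0.015 ≈ 267 to n = 4/0.005 = 800. As a label, 12 = 3% therefore survives at 465 but not at 560 or 650, and 4 = 1% survives across the whole planned range. As a trigger, an actual 1% is still 5 to 7 cases.

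**Step 4: what the 84-day ambiguity can do.** The documents give no expected rate past 84 days, so the rates below are assumptions. X is binomial(n, p), with one look at the end of recruitment.

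| Assumed p | n = 465: X ≥ 4 vs X ≥ 5 | n = 650: X ≥ 4 vs X ≥ 7 |
|---|---|---|
| 0.1% | 0.001 vs <0.001 | 0.004 vs <0.001 |
| 0.5% | 0.21 vs 0.09 | 0.41 vs 0.05 |
| 1.0% | 0.68 vs 0.50 | 0.89 vs 0.47 |

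**Step 5: the denominator during recruitment.** If 1% is taken of those enrolled to date, it is reached at 2 cases among 200 and 3 among 300, which is before the count of 4. Above 400 enrolled it is reached after the count. Which reading is stricter thus depends on the denominator that is left unstated.

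**Step 6: side check on the base.** The SAE rule starts from a stated rate ("Based on evidence that 0.3% of medication abortions have serious adverse events") and labels its interval n = 465. The interval is 0.003 ± 1.96 × √(0.003 × 0.997 / n). At n = 400 this gives −0.24% to 0.84%, as printed; at n = 465 it gives −0.20% to 0.80%. This suggests that the figures in section 14.1 were worked out on about 400. It is an inference and the point does not depend on it.

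**The case against.** The strongest reply is that the 70-day rule is clear enough. It leads with the count and defends the same count in its rationale. On reaching it the team only assesses whether to stop. That stands. A reader might infer that both rules are equally unclear and set 12 cases against 20 at n = 650; with an assumed 2% rate those trigger with probability 0.65 and 0.04. The text does not support treating 20 cases as a live alternative for that rule.

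A reader might also infer that count and percentage disagree at every planned size. That holds only if the percentages are exact; Step 3 shows how much ordinary rounding absorbs.

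Nor are these the only numeric controls on late intake. Section 14.1 also halts the study temporarily after 3 deliveries delayed by more than 7 days, and has every use past 70 days investigated. Section 8.6 sends the research team an automatic notification when intake past 70 days is reported. Cases are therefore acted on individually before either threshold is reached.

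Intake past 84 days may be rare: entry is capped at 63 days, so it needs a delay of more than 21 days, and the US home-use study cited in section 1 reported no intake after 63 days. At an assumed 0.1% the two readings hardly differ. That limits the practical size of the problem but does not settle which reading applies.

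Finally, it can be said that the count is the stricter reading from 465 to 650, so following it errs toward earlier action. This is true for the final total, but nothing in the text requires that reading, and it reverses early in recruitment if the percentage is applied to those enrolled so far.

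**Conclusion.** The point holds in a limited form. Both pairs are exact only at 400, a base that the words used in section 14.1 do not describe and that differs from the 465 named for the SAE rule beside them.

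For the mandatory 84-day stop the inconsistency is substantive: 4 cases by count, against 5 (n = 465) to 7 (n = 650) by percentage of the final total, with neither precedence nor denominator stated. The gap in trigger probability is 0.21 versus 0.09 at 465 and 0.41 versus 0.05 at 650. These figures rest on an assumed 0.5% rate and a single end-of-recruitment look; the gap is negligible at 0.1%.

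For the 70-day assessment the count of 12 is the evident trigger. The error there is the 3% label, which is acceptable after rounding up to n of about 480 and wrong above that (2.1% at 560, 1.8% at 650).

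**What to change.** Reconcile each pair in section 14.1. For each rule, state whether the count or the percentage governs, name the denominator (enrolled, took mifepristone, or analysed), and say whether during recruitment it is the number to date or the final total. Then correct the other figure to match:

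- If the counts govern, 12 cases is 2.6% to 1.8%, and 4 cases 0.9% to 0.6%, of 465 to 650 recruited.
- If the percentages govern, print the corresponding counts for the chosen denominator.
- If 400 is the intended base, say so in place of the present wording, and say what applies when the sample is larger.

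Which threshold is appropriate is for the sponsor to decide; none is proposed here. The cost is about one corrected sentence per rule in a protocol amendment, with no change to data collection or sample size.
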